11.2.2 SERIOUS ADVERSE EVENTS DURING CHEMORADIATION

Serious Adverse Events (SAEs) will be summarized by system organ class and preferred term. A listing of the reasons for considering a SAE will be provided. Narratives of SAEs will be included.

11.2.3 ADVERSE EVENTS DURING CHEMORADIATION ATTRIBUTABLE TO BMX-001

Given that this is an open-label treatment study, adverse events attributable to BMX-001 will only occur in patients within Arm A who receive BMX-001.

For Arm A, the number of subjects with at least one BMX-001 related Treatment Emergent AE (TEAE) will be tabulated by preferred term and MedDRA system organ class. Subjects with more than one BMX-001 related TEAE will be counted only once, at casualty, for each system organ class /preferred term. Multiple TEAEs in a subject will be counted once per system organ class and preferred term. This summary will be sorted by system organ class and decreasing total incidence of preferred term.

11.2.4 OTHER SAFETY MEASURES AND TABULATIONS

All AEs will be listed. A listing of the relationship between system organ class and verbatim text will also be presented.

Listings of the following data will be generated:

- Clinical Laboratory Evaluations: all laboratory values of clinical significance (as defined by site principal investigator) will be listed.
- Vital signs: Vital signs pre and post BMX-001 injection will be summarized.
 Only vital signs of clinical significance as defined by the site principal investigator will be summarized and listed.
- Physical Examinations: Abnormal physical examination findings of clinical significance will be summarized and listed.

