### 5.5.3 BMX-001 Specific Concerns

Subjects meeting any of the following criteria are **ineligible** for study entry:

- 1. Inadequately controlled hypertension (defined as systolic blood pressure >150 mmHg and/or diastolic blood pressure > 100 mmHg) within 28 days of first study treatment
- 2. Active or history of postural hypotension and autonomic dysfunction
- 3. Clinically significant (i.e. active) cardiovascular disease or cerebrovascular disease, for example cerebrovascular accidents ≤ 6 months prior to study enrollment, myocardial infarction ≤ 6 months prior to study enrollment, unstable angina, New York Heart Association (NYHA) Grade II or greater congestive heart failure (CHF), or serious cardiac arrhythmia uncontrolled by medication or potentially interfering with protocol treatment
- 4. History or evidence upon physical/neurological examination of central nervous system disease (e.g. seizures) unrelated to cancer unless adequately controlled by medication or potentially interfering with protocol treatment
- 5. Significant vascular disease (e.g., aortic aneurysm requiring surgical repair or recent arterial thrombosis) within 6 months prior to start of study treatment
- 6. A marked baseline prolongation of QT/QTc interval (e.g., repeated demonstration of a QTc interval >480 milliseconds (ms) (CTCAE grade 1) using the specific/usual choice by clinical center for correction factor.
- 7. A known history of additional risk factors for Torsades de Pointes (TdP) (e.g., congestive heart failure, hypokalemia, known family history of Long QT Syndrome).

For inclusion criteria (Section 5.5.1) #4 and exclusion criteria (Section 5.5.2) #9, final review and determination will be made centrally. The baseline CT or MRI scan will be uploaded to the Duke coordinating center for final confirmation of eligibility. Review the sponsor provided Imaging Manual

for more details about this transfer. Once eligibility is confirmed the site will be notified. Subjects will not be randomized until final eligibility is confirmed.

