### 5.6.2 Risks of BMX-001

Studies have been performed using intravenous infusions of a related metalloporphyrin in multiple models including rats, mice, dogs, guinea pigs, and baboons with the finding of dose-related hypotension [2]. Metalloporphyrin compounds being evaluated are potent, catalytic antioxidants and have the potential to scavenge superoxide within the vascular system and thereby change the balance of superoxide and nitric oxide in the microvasculature. This would augment the vasodilating activity of nitric oxide and lead to hypotension [2]. This has been found in animal models to be a significant, but transient side effect and therefore blood pressure monitoring is essential in this clinical trial of a metalloporphyrin compound. Studies of rats, mice, and monkeys have been performed with BMX-001 and have shown transient, dose-related hypotension. Hypotension is related to plasma Cmax levels and subcutaneous administration significantly reduces the risk of this toxicity in mice and primates (unpublished data per BioMimetix JV, LLC). This hypotensive effect was also found in primates. We have designed this protocol to monitor blood pressure closely.

A summary of the possible adverse side effects that could be associated with BMX-001 administration is below. These possible side effects are dose-dependent, and the relatively low doses of this drug planned in this study have not been associated with side effects in animals other than those related to the color of the injected drug.

The most common side effects (expected to occur in more than 30% of subjects) are:

- Red to brown discoloration of the skin at the injection site which may take up to several weeks to resolve
- Irritation at the site of the injection of the drug under the skin
- Transient tachycardia from study drug

Less common side effects (expected to occur in 10-30% of subjects) are:

- Transient pain at the injection site. This is expected to be related to the concentration of administered drug and the volume administered, rather than subject body size
- Local histamine release which could be caused by study drug. This could cause pruritus (itching), erythema (redness), edema (swelling), urticaria (welts). This is expected to resolve within a couple of hours of injection

Rare side effects (expected to occur in less than 10% of subjects) are:

- Temporary hypotension (low blood pressure)
- Malaise or "not feeling well" for a few hours
- Prolongation of the QTc interval

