### 9.1.3 Safety Considerations

In Phase 1, no hypotension was found in the dose chosen for Phase 2. However, because of the development of transient hypotension in rat models, patients will undergo monitoring before and at 5 (+/-2), 15 (+/-3), 30 (+/-5), and 60 minutes (+/- 5) minutes after the BMX-001 injections on the loading dose day and 5 (+/-2), 15 (+/-3), 30 (+/-5) on all other days of BMX-001 injections. This will

include the following vital signs: heart rate, oxygen saturation, and blood pressure. Injection site reaction will also be reviewed. In summary, patients will be observed for at least 60 (+/-5) minutes after the subcutaneous injection of BMX-001 on the loading dose day and at least 30 (+/- 5) minutes on the maintenance dose days. This observation will include collection of heart rate, oxygen saturation, blood pressure, as well as injection site reaction.

In primate studies, the primary toxicity seen was skin reaction/irritation and/or transient skin discoloration due to subcutaneous injection. Excretion of the drug was also associated with a red/purple color of urine. Care will be taken to limit the volume of the injections to no more than 1.4 mL per site. Thus a 28 mg/subject (2.8 mL @ 10 mg/mL) or 20 mg/subject (2 mL @ 10 mg/mL) dose will be administered in two equal portions at two different sites. A 42 mg/subject (4.2 mL @ 10 mg/mL) dose will be administered in three equal portions at three different sites. A separate drug product vial, syringe and needle will be used for each injection. Before patients are initiated on any treatments (radiation, TMZ, or BMX-001), patient must be at least 2 weeks from neurosurgical procedure (craniotomy, open biopsy, or stereotactic biopsy). Moreover, there can be no signs of wound-healing problems or infection at the craniotomy/biopsy site.

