19 DESCRIPTION OF TABLES FOR REPORTING

The following tables and figures will be produced, source data listings will be provided

Description	Population		
Summary of Subject Disposition	ITT, Safety, Treated		
Summary of Important Protocol Deviations*	Safety		
DEMOGRAPHICS			
Summary of Demographic Characteristics	ITT, Treated		
SAFETY DATA	1		
Summary of All AEs	Safety		
Summary of TEAEs	Safety		
Summary of BMX-001 Related TEAEs	Safety		
Summary of Baseline AEs	Safety		
Summary of all AEs	Safety		
Summary of SAEs/Deaths	Safety		
Narratives of SAEs	Safety		
Summary of Pre and Post dosing Vital Signs	Safety		
Listing of Abnormal ECG findings post BMX-001 treatment	Safety		
Summary of clinically significant:	Safety		
 Clinical Laboratory Evaluations Physical Examinations: Abnormal physical examination findings 	Safety		
PK*	PK		
OUTCOMES			
os	ITT, Treated		
PFS	ITT, Treated		
Thrombocytopenia	ITT, Treated		
Cognitive Testing	ITT, Treated		
HRQoLs	ITT, Treated		
OTHER			
Treatment Disposition: TMZ, RT, BMX-001	Safety		

Treatment Exposure: TMZ, RT, BMX-001	Safety
Concomitant Medications	Treated
Analysis Sets, including subjects excluded from analysis	All
List of Withdrawals	All

^{*=} BioMimetix will provide

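### SAP 11.2.4 contradicts itself and SAP 19 on whether all pre- and post-injection vital signs, or only those the site investigator flags, are summarised; ECGs get a listing of abnormal findings only

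*SAP*

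**What the plan says.** Under vital signs, SAP 11.2.4 has two consecutive sentences. The first is "Vital signs pre and post BMX-001 injection will be summarized". The second is "Only vital signs of clinical significance as defined by the site principal investigator will be summarized and listed". SAP 19 then lists "Summary of Pre and Post dosing Vital Signs" for the Safety population, with no clinical-significance filter.

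SAP 11.2.4 does not mention ECGs. The one ECG output in the SAP is in section 19: "Listing of Abnormal ECG findings post BMX-001 treatment".

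The protocol collects far more than flagged values. Section 9.1.3 says that "because of the development of transient hypotension in rat models, patients will undergo monitoring before and at 5 (+/-2), 15 (+/-3), 30 (+/-5), and 60" (times in minutes, loading-dose day), and at the same times up to 30 minutes on other dosing days, recording heart rate, oxygen saturation and blood pressure. Table 4 repeats this schedule for Arm A. It also sets ECGs before and 60 minutes after dosing on three days: the loading dose, the first maintenance dose in week 1 and one dose in week 4. Section 13.8.3 has the tracings uploaded to the sponsor's database.

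Section 5.6.2 gives the reasons for monitoring. "Transient tachycardia from study drug" is among the effects expected in more than 30% of subjects, and hypotension and QTc prolongation are among those expected in less than 10%. One grade 3 sinus tachycardia was the Phase 1 dose-limiting toxicity, at the 42 mg loading dose. Section 9.1.4 reports QT prolongation after the 28 mg loading dose, which is the Phase 2 dose.

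**The concern.** The two sentences in SAP 11.2.4 cannot both be followed. A programmer who follows the second tabulates only the readings that a site investigator judged clinically significant. Those investigators know the treatment, and the judgement depends on the reading itself, so the summarised set is chosen on outcome. A modest but consistent fall in blood pressure or rise in heart rate that nobody flags would not appear.

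At stake is the description of the drug's acute haemodynamic effect: how large it is, when it occurs after injection, and how many patients pass a given level. The timed schedule exists to show this. The ECG side has a similar gap, because a listing of abnormal findings gives no estimate of change from pre-dose.

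**Working it through.** The plan states no figure for this point, so there is none to reproduce. The check is a reading of the texts plus illustrative arithmetic.

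**1. Do the documents settle which sentence governs?**
- SAP 11.2.4, first sentence: all pre- and post-injection values.
- SAP 11.2.4, second sentence: flagged values only, for the summary as well as the listing.
- SAP 19: an unfiltered pre- and post-dosing summary. A separate row for clinically significant results covers laboratory evaluations and physical examinations, and vital signs are not in it.
- Protocol 16.5.2.3: adverse-event tabulations only, with no vital-sign analysis. SAP 3 gives the SAP precedence in any case.

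SAP 19 leans towards the unfiltered reading. It gives only a table title, however, and the restricting sentence names summaries explicitly. The conflict remains open.

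**2. What does each reading produce?** Let D be the post-dose minus pre-dose change and c a fixed threshold.
- All readings: the mean of D over dosed patients, and the number of patients beyond c divided by the number dosed.
- Flagged readings: the mean of D among flagged values. This equals the overall mean only if flagging is unrelated to D, which it cannot be. A count beyond c includes only values that are both beyond c and flagged, so it is a lower bound with an unknown shortfall. Dividing by the Safety population gives the proportion flagged, not the proportion beyond c.

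**3. How much data is affected?** Inputs: 17 planned doses (Protocol 9.1.5), that is 1 loading + 16 maintenance; 5 sets on the loading day and 4 on each maintenance day (Protocol 9.1.3, Table 4); 78 Arm A patients who received protocol treatment (SAP 10.3.2).
- Vital-sign sets per patient: 5 + 16 × 4 = 69.
- Total: 69 × 78 = 5,382.
- ECGs: 3 days × 2 = 6 per patient; 6 × 78 = 468 tracings, or 234 pairs.

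These are maxima. They assume that all 78 receive all 17 doses with no missed readings.

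**4. What precision would the full data give?** The 95% half-width for a mean within-patient change at one time point is t(0.975, 77) × SD / √78 = 1.991 × SD / 8.832 = 0.225 SD. The documents give no SD. For assumed SDs of 8, 10, 15 and 20 units the half-widths are ±1.8, ±2.3, ±3.4 and ±4.5 units.

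**5. Why should a QTc table name its correction?** With RR = 60/heart rate, Bazett is QT/RR^(1/2) and Fridericia is QT/RR^(1/3). For an assumed QT of 360 ms:

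| Heart rate (/min) | Bazett (ms) | Fridericia (ms) | Difference before rounding (ms) |
|---|---|---|---|
| 60 | 360 | 360 | 0 |
| 80 | 416 | 396 | 19 |
| 100 | 465 | 427 | 38 |
| 110 | 487 | 441 | 47 |

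At 110/min the same tracing falls on opposite sides of 480 ms. The QT and heart rates are illustrations, not trial data.

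**The case against.** The strongest reply is that the documents already plan the right table. The unrestricted sentence comes first, SAP 19 repeats it without a filter, and SAP 19 keeps its clinically significant results in a different row. On this view the second sentence is loose wording meant for the listing. That is a fair reading, and it rules out the stronger claim that the SAP summarises only flagged values as a settled matter. It does not remove the conflict, because the sentence applies the restriction to the summary too.

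A reader might also infer that the drug's effects cannot be measured, or that their frequency cannot be stated. The documents do not support either. The readings are collected and the tracings are held by the sponsor. SAP 11.2.1 tabulates treatment-emergent events by arm and preferred term regardless of attribution, and SAP 11.2.3 tabulates the BMX-001-related ones. What those tables lack is the size and time course of change, and they count only what sites chose to record as events.

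Nor is the formal safety endpoint lost. The endpoints for secondary objective 3 are proportions of patients with grade 3 or 4 adverse events, and they are unaffected.

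On QTc, a reader might infer that sites will use different corrections and that between-site differences will be artefact. The text behind this, "using the specific/usual choice by clinical center for correction factor", is in an eligibility criterion (Protocol 5.5.3). The SAP is silent on correction, no document says which formula any centre uses, and no between-site comparison is planned. Nothing shows that heart rate is still raised at the 60-minute ECG.

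The risk should also be kept in proportion. Hypotension is listed as rare, Protocol 9.1.3 says none was found in Phase 1 at the dose chosen for Phase 2, and the dose-limiting tachycardia was one patient at a dose not used in Phase 2.

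**Conclusion.** The contradiction is real and should be resolved. If the restricting sentence is followed, up to 5,382 timed sets reduce to a subset selected by open-label judgement, which supports neither a mean change from pre-dose nor a proportion beyond a fixed threshold. If it is removed, mean changes can be estimated to about ±0.225 SD. The count assumes full dosing and no missed readings in 78 patients, and the precision assumes one complete pre/post pair per patient at the time point.

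The ECG point is secondary. The SAP plans no summary of QTc or heart-rate change and states no correction formula for analysis. This is a gap in commitment, not evidence of bias between sites.

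Even after a fix, the result is a within-patient description of Arm A. Arm B has vital signs only on history-and-physical days and an ECG only at screening, so there is no matched comparison. The primary endpoint is untouched.

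**What to change.** In SAP 11.2.4:
- Delete the sentence that limits the vital-sign summary to investigator-flagged values.
- State that observed values and change from pre-dose will be summarised for systolic and diastolic pressure, heart rate and oxygen saturation. Use all Arm A readings, by scheduled time point, separately for loading and maintenance doses.
- Add the number and percentage of patients crossing numeric reporting thresholds, fixed in the SAP before the readings are tabulated.
- Keep the flagged values as an additional listing, and match the SAP 19 row to this text.

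For ECGs, add to SAP 11.2.4 and SAP 19 a table of paired pre- to post-dose change in heart rate and QTc on the three ECG dosing days. Use one correction formula named in advance, where QT and rate are available. If CTCAE categories are shown, first reconcile Protocol 5.5.3, which labels a QTc above 480 ms as grade 1, with Protocol 9.1.4, which gives grade 2 as 481–500 ms.

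The vital-sign change costs SAP wording and a few tables from data already collected. The ECG table may also need data entry: up to 468 tracings if QT and rate are not already in the database. No new patient procedure is involved.

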12 SECONDARY OBJECTIVE: PROGRESSION-FREE SURVIVAL

The fourth secondary objective is to assess the effect on progression-free survival (PFS) of standard RT and TMZ in combination with BMX-001 compared to standard RT and TMZ alone in newly diagnosed HGG patients.

12.1 ENDPOINT

Progression-Free Survival (PFS) is defined as the time between initiation of protocol treatment and disease progression or death. If the patient remains alive without disease progression, then PFS will be censored at last follow-up. Analyses similar to those described for OS will be generated for PFS.

12.2 METHOD OF ANALYSIS

The primary analysis of PFS will consider all patients, and consider them in their assigned treatment arm regardless of compliance. This approach to analysis is consistent with an intent-to-treat analysis approach.

As with survival, Kaplan-Meier methods will be used to graphically describe the distribution of PFS among patients within the BMX-001 treated group (Arm A) and within the control group (Arm B). Median PFS, as well as 6- and 12-month estimates of PFS will be estimated from the Kaplan-Meier curve. A logrank test will compare arms with respect to the PFS outcome.

12.3 ADDITIONAL ANALYSES

Analyses similar to those described in Section 8.5 will be conducted for PFS, including analyses within subgroups of patients defined by grade, histological subtype, and tumor markers which have been captured in the study database. Analyses will also explore the interaction between clinical factors and treatment assignment on the PFS outcome.

13 SECONDARY OBJECTIVE: RADIOGRAPHIC RESPONSE

The fifth secondary objective is to assess radiographic response in newly diagnosed HGG patients treated with standard RT and TMZ in combination with BMX-001 compared to standard RT and TMZ alone.

13.1 ENDPOINT

Radiographic response will be determined by brain MRI evaluations for assessment based on the RANO criteria. The radiographic response rate is defined as the proportion of patients of with a complete or partial response.

13.2 METHOD OF ANALYSIS

The response rate within each arm will be calculated and compared using a chisquare test or an exact chi-square test. Exact binomial confidence intervals will be generated for each response rate estimate.

The initial analysis of response rate will focus on the ITT patient population. Those patients who did not receive treatment, or did not have a follow-up radiographic assessment will be included in the denominator for the calculation of response rate. These patients will not be counted a responders.

13.3 ADDITIONAL ANALYSES

Additional analyses will describe the response rate within patient subgroups defined by arm and WHO grade. Response rate will also be summarized within the treated patient population.

14 SECONDARY OBJECTIVE: PHARMACOKINETICS

The sixth secondary objective is to characterize the repeated-dose pharmacokinetic profile of BMX-001 when delivered in combination with RT and TMZ in newly diagnosed HGG patients.

Samples were obtained from the first 6 patients at Duke that are randomized to Arm A. Drug pharmacokinetics were obtained on Day 8 or the next day when drug is administered and Day 36 or the next day when drug was administered during the chemoradiation phase. Measures were obtained at the following time-points will be summarized: Pre-Dose, 0.5 hour, 1 hour, 2 hours, 6 hours and 24 hours.

15 EXPLORATORY OBJECTIVE: HEALTH-RELATED QUALITY OF LIFE (HRQoL)

The first exploratory objective is to describe patient-reported outcomes of HRQoL in newly diagnosed HGG patients treated with standard RT and TMZ in combination with BMX-001 compared to standard RT and TMZ alone.

HRQoL was assessed by the Functional Assessment of Cancer Therapy-Brain (FACT-BR) scale. The FACT-BR (version 4) contains subscales for

- Physical well-being (7-items)
- Functional well-being (7-items)
- Emotional well-being (6-items)
- Social/family well-being (7-items)
- Brain cancer subscale (BCS; 23-items) which assess symptoms commonly reported by brain cancer patients [27].

Cancer-related fatigue was assessed by the 13-item Fatigue Scale using the Functional Assessment of Cancer Therapy-Fatigue (FACIT-Fatigue) subscale, version 4 [67].

Cognitive problems was assessed using version 3 of the Functional Assessment of Cancer Therapy-Cognition (FACT-Cog) subscale [68]. This includes subscales for:

- Perceived cognitive impairments (20 items)
- Comments from others (4 items)
- Perceived cognitive abilities (9 items)
- Impact of quality of life (4 items).

Beck depression inventory (BDI) was used to evaluate for underlying depressive symptoms. We used the revised version (BDI-II) and the scores will range from 0 (no depression) to 63 (severe depression) [69]. The BDI contains 21 questions in regards to mood symptoms and is multiple-choice and self-reported.

Exercise behavior was assessed using the Godin Leisure questionnaire [70].

HRQoL PROs questionnaires were obtained at screening, after standard RT and TMZ (within 2 to 4 weeks), and approximately every 8 weeks when a subject returned for a Standard of Care visit during adjuvant TMZ.

15.1 ENDPOINT

Though the study is a longitudinal analysis, the initial focus of the analyses of this objective is an examination of the mean change in HRQoL between baseline and week 24 (occurs after completion of RT) within each treatment arm of the treated subjects.

There is variability in the timing of follow-up measurements. For the purpose of this analysis a +/- 4 week window will define the 24 week assessment.

